9.1 Will the subjects be asked for informed consent?

Yes (*Upload Patient Information Letter and Informed Consent*)
 No, only anonymous data is used, i.e. the data can never be traced back to an individual subject
 No, this research will be performed under the exception consent
(Upload form Care for data Template, in Dutch: Formulier uitzondering toestemming)
 Other (e.g. partly, indirectly) *Please describe the situation*
The digital survey that has been constructed by the EAU and IFSBH will be distributed through the IFSBH and local patient organizations to their members by email and newsletter. A link to the digital survey can be found in this correspondence.

A short introduction with the purpose of the survey and a question whether patients agree that their data will anonymously be used for research is the start of the digital survey. When patients answer no to this question, the digital survey is immediately ended. The data gathered cannot be traced back to the individual respondents.

9.2 If no, exception consent: Participation is voluntary, people that do not want to participate will not complete the questionnaire. They can withdrawal at any time and the responses will be deleted.

10. Handling and storage of data and images

10.1 The data is collected anonymous and it will not be possible to trace back to one specific patient.

10.2 The data will be stored in the Castor information system. Only anonymous data will be used, so it will not be possible to trace back to an individual patient.

11. Amendments

Amendments are changes made to the research after a favourable opinion by the NWTC has been given. All amendments will be submitted to the NWTC that gave the favourable opinion.

Substantial amendments must be approved by the NWTC before they can be implemented.

12. Publication

Do you have the intention to submit the study results in a manuscript for publication in a journal:

Yes

No, *please motivate*

13. References

2. Radmayr C, et al: EAU Pediatric urology guidelines, EAU Guidelines. Edn. presented at the EAU Annual Congress Amsterdam 2022. ISBN 978-94-92671-16-5

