4.2 Inclusion criteria

In order to be eligible to participate in this study, a subject must meet all of the following criteria:

- Must have spina bifida
- Must be able to complete the digital survey, with help of caregivers allowed.
- Speak one of the nine available languages:
 - o English,
 - o Spanish,
 - o German,
 - o Italian,
 - o French,
 - o Danish,
 - o Greek,
 - o Turkish,
 - o Dutch

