5.1 A digital survey has been created on Surveymonkey: <https://www.surveymonkey.com/r/7WSB9S9>

This digital survey includes a primary survey regarding basic demographic features, medical treatment and organization of care. This survey was constructed by the EAU guidelines panel and the IFSBH patient representatives. The second part of the digital survey includes two validated questionnaires. The QUALAS is a validated questionnaire regarding quality of life in patients with spina bifida. There are two different versions for the ages 8-12 and 13-18 years. To evaluate sexuality the IIEF-5 (for boys) and the FSFI-6 (for girls) are used. These questionnaires are validated and are used in patients with spina bifida to evaluate sexual function as standard of care. Only children aged 13 years or older will be asked if they want to answer questions about sexuality and if they answer yes they will be asked for which gender they want to answer questions about their sexuality. After this they'll get the IIEF-5 or FSFI-6 questionnaire.

This digital survey is available in nine languages: English, Spanish, German, Italian, French, Danish, Greek, Turkish and Dutch.

The link to surveymonkey will be distributed by the IFSBH and local patient organizations among their members.

After the data have been collected, the general results of the survey will be evaluated and interpreted with a sounding board group. When patients participate with the digital survey they will not be involved in the sounding group. This sounding board group will consist of children/adolescents/adults with spina bifida who are representatives from the patient organization IFSBH and panel members of the EAU. This sounding board group will meet for a day. Finally, the results will be used to update the EAU Pediatric Urology guidelines.

5.2 This is a demographic study. Patients will not receive any difference in treatment.

5.3 The survey only has to be completed once and is completely voluntary. The questionnaire will take around 15 minutes to complete. It will not influence their own treatment.

5.4 There are no known risks of participating in the study given the fact that involves only the completion of questionnaires and data about standard of care. Also, all responses will be anonymous and completely voluntary. No personal identifying information will be used when reporting the data.

6 Unexpected discoveries

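### Does the deletion promise in section 9.2 discard completed QUALAS scores from teenagers who stop part-way?

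*Combined protocol and SAP*

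**What the plan says.** Section 9.2 (Recruitment and consent) is the field for research under the consent exception. After saying that participation is voluntary, it states that "people that do not want to participate will not complete the questionnaire", and then: "They can withdrawal at any time and the responses will be deleted". It does not define withdrawal.

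Section 9.1 says the survey opens with a consent item: "a question whether patients agree that their data will anonymously be used for research is the start of the digital survey". A no ends the survey. The same section adds: "The data gathered cannot be traced back to the individual respondents". Sections 10.1 and 10.2 repeat that responses are anonymous.

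Section 5.1 describes a primary survey on demographics, treatment and organization of care, followed by this: "The second part of the digital survey includes two validated questionnaires". The QUALAS is described first: "There are two different versions for the ages 8-12 and 13-18 years". On the IIEF-5 and FSFI-6 it says: "Only children aged 13 years or older will be asked if they want to answer questions about sexuality". Only those who answer yes receive the items. The order within the second part is not stated outright.

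Section 8.1 makes the QUALAS primary and plans comparisons between countries and across demographic factors. Sections 8.1 and 8.2 name descriptive statistics as the method. Neither mentions unfinished surveys. Section 4.4 aims for 500 patients, with no calculation behind the number.

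**The concern.** If records cannot be traced, a submitted response cannot be found and deleted. The part of the promise that can be carried out is deletion of an unsubmitted survey. On that reading 9.2 stops being only a consent clause and becomes a missing-data rule: whoever stops loses everything entered so far. The sentence before it, which links unwillingness to participate with not completing, encourages this reading.

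The loss could then be selective. The sexuality questions go only to ages 13-18, which is also the age range of the teenage QUALAS version. If they follow the QUALAS, a teenager who leaves there has already supplied the primary outcome, and it would be deleted. Section 4.2 lets caregivers assist ("Must be able to complete the digital survey, with help of caregivers allowed"), so some teenagers may meet these items with a caregiver present. Willingness to continue may also differ between countries, which is the comparison in 8.1. Deleted anonymous answers cannot be recovered, and without counts by section a reader could not judge how many were lost.

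**Working it through.** **The plan's own figure.** The only one is the target of 500. It has no alpha, power, SD, effect size or dropout rate behind it, so there is nothing to reproduce.

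**What the text establishes.**

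| Link needed for the loss | What the document gives |
|---|---|
| Breaking off counts as withdrawal | 9.2 speaks of withdrawal only. It says the unwilling will not complete, not that everyone who fails to complete has withdrawn |
| Sexuality items come after the QUALAS | 5.1 lists the QUALAS first but states no order within the second part |
| Teenagers leave rather than decline | 5.1 gives an opt-in question, so a teenager can say no and still finish |
| Finished QUALAS scores are then excluded | Section 8 is silent |

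All of these must hold. The first three rest on inference. The fourth follows if deletion is applied, and otherwise is left to the analysts.

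**Size if they all hold.** The inputs from the documents are 500 patients and the age bands. The even age spread, the leaving rate p, the difference d between those who stay and those who leave, and the group size are assumptions.

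- Ages 8-18 are 11 single years and 13-18 are 6 of them. Teenagers = 500 × 6/11 = 273.
- Finished QUALAS deleted = 273 × p.
- Standard error inflation = 1/√(1 − p).
- Shift in the teen mean = p × d, with d = 0.5 SD.
- Standard error after deletion, in SD units = 1/√(273 × (1 − p)).

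| p | Deleted | SE inflation | Shift (SD) | SE (SD) | Shift ÷ SE |
|---|---|---|---|---|---|
| 0.02 | 5 | 1.010 | 0.010 | 0.0611 | 0.16 |
| 0.05 | 14 | 1.026 | 0.025 | 0.0621 | 0.40 |
| 0.10 | 27 | 1.054 | 0.050 | 0.0638 | 0.78 |
| 0.20 | 55 | 1.118 | 0.100 | 0.0677 | 1.48 |

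At d = 0.25 SD the shifts and ratios halve. With d = 0.5 SD the shift reaches one standard error at about p = 0.13: 0.13 × 0.5 = 0.065, against 1/√(273 × 0.87) = 0.065. If teenagers are 40% of the sample (200) or 70% (350), the ratio at p = 0.20 is 1.26 or 1.67.

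**Between-country contrast.** Take nine equal groups, borrowing the nine survey languages as a stand-in for countries: 273/9 = 30.3 teenagers each. Let 5% leave in one group and 20% in another, with d = 0.5 SD.

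- Shift = (0.20 − 0.05) × 0.5 = 0.075 SD.
- SE of the difference = √(1/(30.3 × 0.95) + 1/(30.3 × 0.80)) = 0.276 SD.
- Ratio = 0.075/0.276 = 0.27.

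These rates apply to all 273 teenagers. The exposed group is smaller in kind: those who close the survey instead of answering no, and those who opt in and then stop.

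**The case for a change.** The best case for acting is that both readings of 9.2 leave something unsettled. As a right exercised after submission, deletion cannot be delivered. As a rule for those who stop, it removes usable data. The silence of section 8 does not depend on the reading, and a descriptive study still needs a defined denominator. Even if the sexuality items came before the QUALAS, deletion on stopping would still remove primary-survey answers that feed the secondary parameters. The opt-in question limits the exposure without removing it. A sentence in 8.1 would be cheap.

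Much of this stands. The promise and the anonymity statements do not fit together after submission, and section 8 has no rule for partial surveys. But the first is a consent inconsistency, and neither shows that completed QUALAS scores will be discarded. The analysis sentence would record what an analyst of a descriptive survey would do anyway: use each completed questionnaire that was not withdrawn, and show the denominator for each table. Such a rule may also sit in the Data Management Plan, consent text or platform settings, which were not available.

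The changes that would alter what is collected are not clear gains. Keeping answers from minors who close the page without choosing deletion would, on the very reading that creates the concern, reverse a protection promised to them. A submit step after the QUALAS would need new platform functions and text in nine languages. Either would help only while the survey is open, and section 4.6 plans three months of availability.

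**Conclusion.** The concern does not call for a change to the plan. The text is loose: 9.2 leaves withdrawal undefined and promises a deletion that cannot be carried out after submission, and section 8 does not mention partial surveys. But selective loss of the primary outcome requires a particular reading of a consent clause, an item order that is not stated, and departures that the opt-in question already gives teenagers a way to avoid.

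Under the assumptions above, the effect is negligible at 2% leaving and small against sampling error for a contrast between two countries (0.27 standard errors). It is noticeable only for the pooled teenage mean, at 10-20% leaving combined with a 0.5 SD difference (0.78 to 1.48 standard errors). The documents give no leaving rate, no difference between leavers and stayers, no age split and no country sizes, so these figures are illustrations.

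Analysts can fill the gap by analysing each completed QUALAS that was not withdrawn and by reporting, by age band and country, how many started, completed the QUALAS and stopped in each section. How to treat a minor who closes the page is a trade-off between data and consent, and it belongs to the review committee (NWTC).
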